12.3 Screen Failure

Subjects will be allowed to repeat any single screening assessment/procedure once, if necessary, if it is within the screening window. The subject will not be considered a screen failure unless the repeat assessment/procedure results do not meet eligibility criteria. The period from starting screening related procedures at the Screening Visit to the Baseline Visit must not exceed 28 days, inclusive of any repeat screening procedures.

Subjects who do not meet all of the eligibility criteria at the Screening or Baseline Visits will be deemed a screen failure and the reason for the screen failure will be documented. A subject who is a screen failure at the Screening or Baseline Visit may be rescreened. The subject must repeat all screening procedures. The period from the start of rescreening related procedures to the first dose of study drug must not exceed 28 days. Subjects may be rescreened only once.

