12 SELECTION OF SUBJECTS

12.1 Inclusion Criteria

Subjects must meet all of the following criteria for inclusion in the study at the Screening Visit and the Baseline Visit.

1. Subjects must be adequately informed and understand the nature and risks of the study and must be able to provide a signature and date on the ICF.
2. Subjects must be ≥ 18 years of age at Screening Visit and can be male or female.
3. Female subjects must be of nonchildbearing potential (history of hysterectomy, bilateral oophorectomy, or postmenopausal with no history of menstrual flow in the 12 months prior to the Screening Visit), or if of childbearing potential must be nonpregnant, nonlactating and agree to use effective contraception with a male partner throughout study participation (through the Follow-up Visit). Acceptable forms of contraception include hormonal measures (oral contraceptive pills, contraceptive patch, contraceptive ring, injections), intrauterine devices, double barrier method (condom plus diaphragm, condom or diaphragm plus spermicidal gel or foam), and abstinence.
4. Male subjects with a female partner of childbearing potential must have been surgically sterilized (vasectomy) or agree to use a double barrier method for contraception (condom plus diaphragm, condom or diaphragm plus spermicidal gel or foam) or remain abstinent throughout their study participation (through the Follow-up Visit).
5. Subjects must meet the criteria for RA as defined by the 2010 ACR/EULAR classification at the Screening Visit ([Aletaha et al, 2010](#)).
6. Subjects must have persistently active RA defined as a DAS28-ESR > 3.2 despite treatment with required biologic/nonbiologic DMARD(s) and a corticosteroid as defined below at the Screening and Baseline Visits.

7. Subjects must have been on a corticosteroid in the 12 weeks prior to the Screening Visit and on a stable dose of 5 mg to 10 mg of prednisone (or prednisone equivalent) for 4 weeks prior to the Screening Visit.
8. Subjects must have been on 1 of the following:
 - MTX \leq 20 mg per week and 1 additional allowed biologic or nonbiologic DMARD for at least 12 weeks prior to the Screening Visit and must remain on those doses throughout the study, OR
 - One allowed biologic DMARD for at least 12 weeks prior to the Screening Visit and must remain on that dose throughout the study.

Table 12-1 Allowed DMARDs

Allowed Nonbiologic DMARDs	Allowed Biologic DMARDs

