14.1 Screening Visit (Study Days -28 to -1) Procedures/Assessments

Screening assessments must be performed within 1 to 28 days prior to the Baseline Visit.

The following procedures will be performed at the Screening Visit:

- Informed consent.
- Inclusion/exclusion criteria.
- General Health Visual Analog Scale (VAS).
- Medical and surgical history.
- Demographics.
- Complete physical examination.
- 28 Joint Count.
- Height and Weight.
- Vital signs.
- Clinical laboratory tests.
- HbA1c.
- ESR and C - reactive protein (CRP).
- Serum pregnancy test.
- Hepatitis serology.

- IGRA test for TB.
- Contact the Interactive Phone/Web Response System (IXRS) and confirm disease activity.
- Adverse events and concomitant medications.

Subjects will be allowed to repeat any screening procedure once, if necessary, if it is within the screening window.

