20.3 Endpoints

20.3.1 Primary Efficacy Endpoint

The primary efficacy endpoint will be the proportion of subjects with DAS28-ESR < 3.2 at Week 12.

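### Retesting a low DAS28-ESR at entry, with one 3.2 cut for both entry and response, modestly inflates the uncontrolled Week 12 LDA rate

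*Combined protocol and SAP*

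**What the plan says.** **Entry.** Section 12.1, criterion 6: "Subjects must have persistently active RA defined as a DAS28-ESR > 3.2 despite treatment". The lead-in to that section applies every criterion twice: "Subjects must meet all of the following criteria for inclusion in the study at the Screening Visit and the Baseline Visit".

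**Retesting.** Section 12.3: "Subjects will be allowed to repeat any single screening assessment/procedure once, if necessary, if it is within the screening window". It continues: "The subject will not be considered a screen failure unless the repeat assessment/procedure results do not meet eligibility criteria". Section 14.1 gives the same permission without the word for one assessment only: "Subjects will be allowed to repeat any screening procedure once, if necessary, if it is within the screening window". Section 12.3 adds "A subject who is a screen failure at the Screening or Baseline Visit may be rescreened", limited by "Subjects may be rescreened only once". Section 17 names the 28 Joint Count, General Health VAS and ESR as the DAS28-ESR components. All three are on the Section 14.1 screening list, and none is excluded from the repeat rule.

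**Response.** Section 20.3.1 defines the primary endpoint as "the proportion of subjects with DAS28-ESR < 3.2 at Week 12". No minimum fall from entry is required.

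**Design and success rule.** In Part 1 everyone receives open-label Acthar (Section 11.1). The synopsis (Statistical Methods, Efficacy) declares success if the lower 95% confidence bound for the LDA proportion is at least 10%.

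**The concern.** A subject who scores above 3.2 has no reason to be retested, while one at or below 3.2 does. When a passing repeat replaces the failed value without averaging, the retested entrants are enriched for scores that were high by chance. Some of them will fall below 3.2 at Week 12 with no treatment effect, because the response cut is the entry cut with no gap.

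The route is practical. Joints are counted by the investigator or a designee (Section 17.1), ESR is run at the site (Section 17.4), and IXRS calculates the score from the entered components (Section 15.1).

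In a controlled trial this drift would occur in both arms and cancel. Part 1 has no control, so it is counted as Acthar response and enters the comparison with 10%. A second consequence is that some subjects reach Part 2 as responders without having gained anything from Acthar that its withdrawal could remove.

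**Working it through.** **Step 1. The plan's own figure.** Section 20.7 gives power for Part 2 only: 80% versus 50%, 52 per group, two-sided 0.05. With pooled proportion 0.65, z = (0.30 × √52 − 1.96 × √(2 × 0.65 × 0.35)) / √(0.8 × 0.2 + 0.5 × 0.5) = (2.163 − 1.322) / 0.640 = 1.31, so power is 90.6%. The stated 90% reproduces. The available text gives no power figure for the primary endpoint.

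**Step 2. Count needed for success.** With N = 232 and an exact (Clopper-Pearson) interval, the lower bound is 0.09998 at 33/232 and 0.1037 at 34/232. So 34 (14.7%) is the smallest passing count. A Wald interval also gives 34, and a Wilson interval gives 33. The planned count is 0.45 × 232 = 104.

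**Step 3. LDA with no drug effect.** Observed score = stable true score + independent visit error. Entry needs a score above 3.2 at Screening and at Baseline. A failed Screening score may be repeated once, and a failed attempt may be followed by one rescreen on the same terms. A failed Baseline score leads only to the rescreen. The outcome is a Week 12 score below 3.2.

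Assumptions not in the documents: candidates' true mean 3.8 to 4.8, true SD 1.0, visit SD 0.4 to 0.6, no dropout. The whole score is redrawn on repeat. Simulations used 1.5 to 2 million candidates per setting. The chance of success is P(X ≥ 34) for X ~ Binomial(232, null LDA).

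| Mean / visit SD | Null LDA, no retesting | Null LDA, every failure uses both routes | Chance of success, no retesting | Chance of success, full use |
|---|---|---|---|---|
| 3.8 / 0.6 | 9.9% | 14.9% | 1.4% | 57% |
| 4.0 / 0.6 | 8.3% | 12.6% | 0.1% | 20% |
| 4.5 / 0.45 | 3.4% | 5.5% | <0.1% | <0.1% |
| 4.8 / 0.4 | 1.9% | 3.2% | <0.1% | <0.1% |

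Retesting adds between about 1 point (4.8 / 0.4) and 14.9 − 9.9 = 5.0 points (3.8 / 0.6). That is roughly 3 to 12 of 232 subjects (0.050 × 232 = 11.6). At mean 4.3 or more the chance of success stays below 1% even at full use.

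**Step 4. Less than full use, and dropout, at 3.8 / 0.6.**
- Half of failing subjects use each route: null LDA 12.5%, chance of success 19%.
- A quarter use each route: 6%.
- Full use, with an assumed 15% dropout counted as non-LDA: 14.9% × 0.85 = 12.7%, chance of success 21%.
- Half use with the same dropout: 3.5%.

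**Step 5. Where the drift comes from.** At 3.8 / 0.6, 9.9 of the 14.9 points, about two thirds, are present with no retesting. The shared cut is the larger source.

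**Step 6. Part 2.** The share of entrants whose true score is already below 3.2 rises from 3.3% to 7.6% at 3.8 / 0.6, and from 1.1% to 2.8% at 4.3 / 0.4.

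**The case against.** The strongest reply is that the plan already limits the problem. There is one repeat and one rescreen, not open-ended retesting. Section 12.3 confines the repeat to a single assessment, so redoing the whole composite is not clearly allowed, and a failed Baseline score has no express repeat. The score must exceed 3.2 on two occasions. At mean 4.5 and visit SD 0.45 this lowers null LDA from 5.2% with one qualifying look to 3.4% with two, although full retesting brings it back to 5.5%. All of this stands, and the full-use figures are therefore upper limits.

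Four stronger readings are tempting, and the documents do not support them.

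- *A score can be retested until it passes.* Sections 12.3 and 14.1 cap both routes at one.
- *Everyone admitted on a high error falls back below 3.2.* Only some do. The table gives the whole null rate, including the part due to the shared cut.
- *An inactive drug would probably succeed.* The 57% needs a candidate mean of 3.8, visit SD 0.6, every failing subject using both routes, and no dropout. None of these is in the documents, and Section 20.7 itself groups dropouts with non-achievers.
- *Part 2 is biased toward Acthar.* Part 2 is randomized 1:1 and double-blind (Section 11.1), so such subjects may dilute the contrast but do not favour Acthar.

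It is also fair to say that removing repeats leaves most of the drift, and that barring rescreening would exclude patients whose disease has truly worsened. Both points shape the remedy. Finally, Section 20.1 and part of the efficacy analysis are missing from the available text, so nothing is claimed about whether the 10% bound was justified.

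**Conclusion.** The concern holds as a modest upward bias in the primary LDA rate. Its direction follows from the text: low scores alone are retested, a passing repeat stands, entry and response share one cut, and Part 1 has no control.

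Its size rests on assumptions about case mix and visit noise. Over the range examined, noise alone gives about 2-10% LDA without retesting and at most 3-15% with it. The success verdict is vulnerable only if many candidates lie near 3.2. At mean 3.8 and visit SD 0.6, the chance that an inactive drug passes is about 1% without retesting, 19% at half use and 57% as an upper limit. If the planned 45% is achieved, the trial passes regardless, and the effect is confined to some overstatement of the rate. The point merits a wording change and two extra analyses, not a change of primary endpoint.

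**What to change.** 1. In Sections 12.3 and 14.1, exempt the 28 Joint Count, General Health VAS and ESR from the repeat rule unless a result is missing or technically invalid. Align the two sections on whether one assessment or any assessment may be repeated.
2. Keep the single rescreen. Flag subjects who qualified after a DAS28-ESR repeat, or after a rescreen prompted by a score of 3.2 or less. Report the primary endpoint without them as a sensitivity analysis.
3. Because most of the drift comes from the shared cut, add a supportive analysis requiring DAS28-ESR below 3.2 plus a prespecified minimum fall from the mean of the Screening and Baseline scores. A fall above 1.2 is one example. It is an assumption, since the plan uses 1.2 only in the Part 2 flare rule. Leave the primary endpoint unchanged.

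The data are already collected at both visits (Table 7-1). The cost is protocol wording, two tables and a few more screen failures. The supportive rate will be lower than the primary rate, partly because it excludes some genuine responders who enter near 3.2. As a rough guide, a simulation set to 45% LDA put 4 to 13 points of it in subjects falling 1.2 or less from Baseline, leaving about 32-41%.

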13 PRIOR AND CONCOMITANT MEDICATION/NONDRUG THERAPIES

The start and stop date, dose, unit, frequency, route of administration, and indication for all prior (taken within the 30 days prior to the first dose of study drug) and concomitant medications and nondrug therapies (eg, blood transfusions, oxygen supplementation) received will be recorded.

In addition, all prior treatments for RA will be recorded with start and stop date, dose, unit, frequency and route of administration.

In addition, opioid use for pain management is allowed during the study, however, it cannot be used in the 48 hours prior to each study visit. Non-steroidal anti-inflammatory drugs for pain management are allowed during the study, however, subjects must have been on the medication for at least 4 weeks prior to the Screening Visit and remain on a stable throughout the study.

13.1 Prohibited Concomitant Medications/Nondrug Therapies

The following medications/ nondrug therapies will not be permitted during the study:

- Intraarticular corticosteroids.

- Live or live-attenuated vaccines.
- Enteral or parenteral immunosuppressive medications including, but not limited to azathioprine, cyclophosphamide, cyclosporine, tacrolimus, mycophenolate mofetil, rituximab (or other B-cell inhibitors).
- Any investigational drug, device, or procedure administered as part of a research study.

If any prohibited medication is taken during the study, all pertinent information will be recorded in source documents and the electronic case report form (eCRF). The designated study medical monitor (MM) must be informed immediately so the sponsor may determine whether to continue the subject in the study.

14 PROCEDURES/ASSESSMENTS

The schedule of study procedures is summarized in the Schedule of Study Events ([Table 7-1](#)).

14.1 Screening Visit (Study Days -28 to -1) Procedures/Assessments

Screening assessments must be performed within 1 to 28 days prior to the Baseline Visit.

The following procedures will be performed at the Screening Visit:

- Informed consent.
- Inclusion/exclusion criteria.
- General Health Visual Analog Scale (VAS).
- Medical and surgical history.
- Demographics.
- Complete physical examination.
- 28 Joint Count.
- Height and Weight.
- Vital signs.
- Clinical laboratory tests.
- HbA1c.
- ESR and C - reactive protein (CRP).
- Serum pregnancy test.
- Hepatitis serology.

- IGRA test for TB.
- Contact the Interactive Phone/Web Response System (IXRS) and confirm disease activity.
- Adverse events and concomitant medications.

Subjects will be allowed to repeat any screening procedure once, if necessary, if it is within the screening window.

14.2 Baseline Visit (Week 0) and First Dose Procedures/Assessments

Predose evaluations will occur prior to the first dose of study drug.

The investigator or designee will complete the following procedures predose:

- Inclusion/exclusion criteria review; subject must meet all eligibility criteria at screening and baseline.
- Efficacy Questionnaires: General Health (VAS), Patient Assessment of Pain (VAS), Patient Global Assessment of Disease Activity (VAS), Patient Assessment of Physical Function assessed using the Health Assessment Questionnaire- Disability Index [HAQ-DI]), Functional Assessment of Chronic Illness Therapy- Fatigue Scale (FACIT-F) and Physician Global Assessment of Disease Activity (VAS).
- Work Productivity and Activities Impairment (WPAI).
- Current medical condition review.
- Limited physical examination.
- 28 Joint Count.
- Weight.
- Vital signs.
- Clinical laboratory tests.
- ESR and CRP.
- Urine pregnancy test.
- Vectra Disease Activity (Vectra[®] DA) sample.

- Serum and urine samples for [REDACTED]
[REDACTED]
[REDACTED]
[REDACTED] and urine creatinine.
- Subject diary training.
- Contact IXRS and confirm disease activity eligibility.
- Dispense study drug kits.
- Study drug administration under supervision of study staff and observation for at least 1 hour thereafter. Administration of all other doses will be done at home by the subject/caregiver.
- Adverse events and concomitant medications.

14.3 Week 4 (\pm 5 days) and 8 (\pm 5 days) Procedures/Assessments

- Efficacy Questionnaires.
- WPAI.
- Current medical condition review.
- Limited physical examination.
- 28 Joint Count.
- Weight.
- Vital signs.
- Clinical laboratory tests.
- ESR and CRP.
- Urine pregnancy test.
- Hospital admissions, emergency department (ED) visits, and nonstudy outpatient visits.
- Subject diary review.
- Study drug accountability.
- Contact IXRS and confirm disease activity eligibility.
- Dispense study drug kits.

- Adverse events and concomitant medications.

14.4 Week 12 (\pm 2 days) Procedures/Assessments

- Efficacy Questionnaires.
- WPAI.
- Current medical condition review.
- Limited physical examination.
- 28 Joint Count.
- Weight.
- Vital signs.
- Clinical laboratory tests.
- HbA1c.
- ESR and CRP.
- ██████████.
- ██████████/urine creatinine samples.
- Urine pregnancy test.
- Hospital admissions, ED visits, and nonstudy outpatient visits.
- Subject diary review.
- Study drug accountability.
- Contact IXRS and confirm disease activity eligibility.
- Dispense study drug kits (if appropriate).
- Adverse events and concomitant medications.

14.5 Week 16 (\pm 5 days) and 20 (\pm 5 days) Procedures/Assessments

- Efficacy Questionnaires.
- WPAI.
- Current medical condition review.
- Limited physical examination.
- 28 Joint Count.
- Weight.

- Vital signs.
- Clinical laboratory tests.
- ESR and CRP.
- Urine pregnancy test.
- Hospital admissions, ED visits, and nonstudy outpatient visits.
- Subject diary review.
- Study drug accountability.
- Contact IXRS and confirm disease activity eligibility.
- Dispense study drug kits.
- Adverse events and concomitant medications.

14.6 Week 24 (\pm 5 days)/Early Termination Procedures/Assessments

- Efficacy Questionnaires.
- WPAI.
- Current medical condition review.
- Complete physical examination.
- 28 Joint Count.
- Weight.
- Vital signs.
- Clinical laboratory tests.
- HbA1c.
- ESR and CRP.
- [REDACTED]
- [REDACTED]/urine creatinine samples.
- Serum pregnancy test.
- Hospital admissions, ED visits, and nonstudy outpatient visits.
- Subject diary review.
- Study drug accountability.

- Adverse events and concomitant medications.

14.7 Follow-up Visit Procedures/Assessments

The following procedures will be completed at the follow-up visit 28 (\pm 2) days after the final dose of study drug:

- Current medical condition review.
- Limited physical examination.
- Weight.
- Vital signs.
- Clinical laboratory tests.
- Urine pregnancy test.
- Adverse events and concomitant medications.

14.8 Unscheduled Visit Procedures/Assessments

Any time that an unscheduled visit is needed to assess the subject for the study (for example, for an adverse event), the following minimum evaluations must be completed:

- Current medical condition review.
- Limited physical examination.
- Weight.
- Vital signs.
- Adverse events and concomitant medications.

15 INVESTIGATIONAL MEDICINAL PRODUCT (Study Drug)

15.1 Methods of Assigning Subjects to Treatment Groups

The investigator or designee will contact IXRS to register subjects at screening. The subject's identification (ID) number will be determined by the IXRS and will be used to identify the subjects for the duration of the study within all systems and documentation. Subject identification numbers will consist of 7 digits: [REDACTED]

A subject ID number will not be assigned to more than 1 subject. If a subject is not eligible to receive treatment, or should a subject discontinue from the study, the subject ID number cannot be reassigned to another subject.

In the event that a subject is rescreened within the screening window, they do not need a new subject ID number. At Baseline, qualified subjects who meet all of the eligibility criteria will be enrolled into the study.

The investigator or designee must contact the IXRS to report subjects as a screen failure if the subject does not meet eligibility criteria predose.

The investigator or designee must contact IXRS to record each subject visit, to receive the study drug kit assignments, and to report any subject status changes. At visits where it is required, components of the DAS28-ESR (swollen joint count, tender joint count, ESR, General Health VAS) will be entered at into IXRS and the DAS28-ESR will be calculated.

The investigator must maintain a subject master log linking the subject ID to the subject's name. The investigator must follow all applicable privacy laws in order to protect a subject's privacy and confidentiality. Information that could identify a subject will be masked on material received by the sponsor.

15.2 Emergency Identification of Investigational Medicinal Product

In case of an emergency during the Randomized Maintenance Period, when knowledge of the investigational product assignment is required for the medical management of an individual subject, the investigator may obtain the treatment assignment of the subject experiencing the emergency. The treatment blind for that subject may be broken by accessing the IXRS using instructions provided. The investigator must notify the sponsor's MM or physician designee immediately after determining that it is necessary to unblind the treatment assignment. The investigator and sponsor should make every effort to document and limit the people who are unblinded to the subject's treatment assignment. The investigator must also indicate in source documents and in the eCRF that the blind was broken and provide the date, time, and reason for breaking the blind.

15.3 Dosing Procedures

The following treatments will be administered:

- Weeks 0 to 12: Acthar 1 mL (80 U) SC 2x/week.
- Weeks 13 to 24: Acthar 1 mL (80 U) SC 2x/per week **OR** Placebo 1 mL SC 2x/week.

Throughout the trial, study drug cannot be taken on 2 consecutive days and cannot be taken more than 3 days apart.

Both Acthar and the placebo are supplied as 5 mL multidose vials. Acthar vials contain 80 U of ACTH per mL. The vials should not be over pressurized prior to withdrawing the product. The vials should be warmed to room temperature before using and will be labeled according to all applicable national and local regulations.

The subject or subject's caregiver will administer the first dose of Acthar in the clinic under the supervision of study staff. The subject will remain in the clinic for at least 1 hour postdose to monitor for allergic or anaphylactic reactions. Thereafter, all doses will be administered by the subject or the subject's caregiver at home.

